8.3.3 Pulmonary Rales and Cardiac Third Sound

For the resolution rates of pulmonary rales and cardiac third sound at the time of final IMP administration, the difference and its two-sided 95% CI (exact) between the OPC-61815 16-mg injection group and the tolvaptan 15-mg tablet group will be calculated. The resolution rate is defined as the proportion of patients in whom the symptom is present at baseline and disappeared after IMP administration.

A shift table in changes of the presence of the symptoms from baseline at the time of final IMP administration and each timepoint by treatment group will be prepared.

8.3.4 NYHA Classification

A shift table for the NYHA classification from baseline at the time of final IMP administration and each timepoint by treatment group will be prepared.

For Class II and higher subjects, the proportion of those who have improved from baseline by 1 or more NYHA class at the time of final IMP administration will be calculated for each treatment group to determine the difference between the OPC-61815 16 mg injection group and the tolvaptan 15 mg tablet group and its two-sided 95% CI (exact).

8.4 Subgroup Analyses

For the main analysis of the primary endpoints, subgroup analyses of the following stratified variables will be performed.

Table 8.4-1 Stratified Variables	
Variable	Level
Sex	Female, Male
Age	<65, ≥65

Table 8.4-1 Stratified Variables

Stratified Variables	
Variable	Level
NYHA classification	Class I, Class II, Class III and Class IV
Ischemic heart disease	Yes, No
Type of heart failure	Right Heart Failure, Left Heart Failure, Bi-ventricular Failure,
Use of loop diuretic	Monotherapy with loop diuretic, Loop diuretic + other diuretic
Dose of loop diuretic (Furosemide equivalent)	<80 mg/day, ≥80 mg/day
Category of diuretic *Concomitant use of diuretic drugs other than loop diuretic, thiazide diuretic, and anti-aldosterone drug is not summarized.	Monotherapy with loop diuretic, Loop diuretic + thiazide diuretic, Loop diuretic + anti-aldosterone drug, Loop diuretic + thiazide diuretic + anti-aldosterone drug
Thiazide diuretic	Yes, No
Anti-aldosterone drug	Yes, No
Daily urine volume (baseline)	<1500 mL, ≥1500 mL
Creatinine (baseline)	<2 mg/dL, ≥2 mg/dL
Plasma AVP concentration (baseline)	≤3.1 pg/mL, ≥3.1 pg/mL
Albumin (baseline)	<3 g/dL, ≥3 g/dL

9 Safety Analyses

The following analyses will be conducted on the safety analysis set by treatment group.

9.1 Extent of Exposure

Distributions of the number of subjects on each number of administration days will be calculated. Descriptive statistics of the number of administration days will be calculated.

9.2 Adverse Events

All adverse events (AEs) will be coded by system organ class (SOC) and ICH Medical Dictionary for Regulatory Activities (MedDRA) preferred term (PT). The incidence of the following events will be summarized for all events, by SOC, and by PT.

- Treatment-emergent AEs (TEAEs)
- TEAEs by severity
- TEAEs with an outcome of death

- Serious TEAEs
- TEAEs leading to discontinuations of the IMP

If there are multiple occurrences of the same event in the same period in the same subject, the event with the highest severity will be selected. IMP-related TEAEs will be summarized in the same manner as shown above.

For TEAEs, a summary table will also be created for any TEAE that occurs in 2% or more of subjects in any group.

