3.8.3.2 Documenting the Reasons for Treatment Discontinuation

A subject may discontinue participation in the trial at any time, and the investigator or subinvestigator may discontinue a subject's participation in the trial if medically necessary. Subjects who fall under any of the following must be withdrawn from the trial.

If a subject discontinues treatment, a single reason for the discontinuation (the main reason) will be recorded in the eCRF.

1) Reasons related to AE:

- Subject decides to discontinue because of annoyance or discomfort due to a non-serious AE which is not otherwise determined to be an undue hazard
- AST or ALT value obtained at the trial site or the central laboratory is ≥ 3 times the upper limit of normal (ULN).
- Serum or plasma sodium concentration measured at the trial site or the central laboratory increases by ≥ 12 mEq/L from immediately predose within 24 hours after start of the IMP administration.
- Serum or plasma sodium concentration measured at the trial site or the central laboratory is ≥ 155 mEq/L during the treatment period.
- The onset of drug-induced hypersensitivity is suspected.
- Any severe AESI (feeling abnormal, feeling hot, erythema, hyperhidrosis, pruritus, rash, urticaria, nausea, epigastric discomfort, or dyspnoea) occurs.
- Continuing IMP places the subject at undue risk as determined by the investigator or subinvestigator (eg, a safety concern that is possibly, probably, or likely related to IMP).
 - Serious adverse event
 - Other potentially IMP-related safety concerns or AEs

- 2) Withdrawal of informed consent by the subject (when it is confirmed to be unrelated to AEs)
- 3) Protocol deviations (other than poor compliance with the IMP administration rules)
 - Deviations related to the inclusion or exclusion criteria
 - Deviations related to prohibited or restricted concomitant medications
- 4) Judgment by the investigator or subinvestigator (for the reasons other than an AE)
- 5) Death
- 6) Lost to follow-up
- 7) Pregnancy (see [Section 5.5](#))
- 8) Technical problems (eg, malfunctions of medical devices)
- 9) Premature termination of the entire or part of the trial by the sponsor

If the subject discontinues IMP due to an AE, the investigator, subinvestigator, or other trial personnel, will make every effort to follow the event until it has resolved or stabilized, or until the subject is lost to follow-up or has died. The procedures in [Section 3.8.3.1](#) must be followed.

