In the clinical development of tolvaptan for the treatment of cardiac edema, there were 2 placebo-comparison trials conducted for tolvaptan 15-mg tablet: a phase 2 trial (156-03-001) and a phase 3 trial (156-06-002). Regarding the change in body weight (kg) on the morning after Day 5 of treatment (LOCF) in those 2 trials, from an analysis of covariance (ANCOVA) model analysis performed using body weight (kg) at baseline as a covariate, the least-square mean of the difference (treatment difference) between the tolvaptan 15-mg tablet group and the placebo group was respectively -0.99 (95% CI: -1.57 to -0.42) and -0.96 (95% CI: -1.37 to -0.55). Referring to the upper limit of those

CIs, the reliably expected (at 95% probability) minimum difference in body weight decrease (maximum difference in body weight) between the tolvaptan 15-mg tablet group and the placebo group was considered to be in the range of 0.42 to 0.55. The non-inferiority margin for the present trial was therefore set at 0.48, which corresponds to half of the treatment difference of 0.96 between the tolvaptan 15-mg tablet group and the placebo group in the tolvaptan phase 3 trial.

Setting the non-inferiority margin at 0.48, the detection power at 90%, and the significance level at 5%, and using the value for up until the morning after Day 5 of treatment in the tolvaptan 15-mg tablet in the tolvaptan phase 3 trial to set the mean \pm SD change in body weight from baseline at time of final administration at -1.30 ± 1.25 for both the tolvaptan 15-mg tablet group and the OPC-61815 16-mg injection group, the number of subjects required for this trial was determined to be 288 (144 subjects per group).

5 Statistical Analysis Datasets

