8.1.1 Primary Efficacy Analysis

Main analysis is an analysis of the primary endpoint using an ANCOVA model with treatment as a fixed effect factor and baseline body weight as a covariate. The least square mean difference and its two-sided 95% CI (based on the t distribution) between the OPC-61815 16-mg injection group and the tolvaptan 15-mg tablet group will be calculated. The non-inferiority of OPC-61815 16-mg injection to tolvaptan 15-mg tablet will be confirmed when the upper limit of the CI does not exceed 0.48.

At each time point, the measured values, changes, and percent changes in body weight from baseline will be summarized by treatment group using descriptive statistics.

Using the main analysis model excluding baseline body weight, the least-square mean of the difference between the OPC-61815 16-mg injection group and the tolvaptan 15-mg group and its two-sided 95% CI will also be calculated.

For changes in body weight from baseline, a timecourse (mean \pm SD) from Day 1 of treatment period to follow-up will be created for each treatment group.

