9.3 Clinical Laboratory Data

Clinical laboratory data obtained from central measurements will be used.

For hematology, serum chemistry (excluding PAP and TRACP-5b), and urinalysis in the protocol “Table 3.7.3.2-1 Clinical Laboratory Assessments”, the following will be summarized.

For clinical laboratory test parameters other than qualitative urinalysis, measured values and changes from baseline at each time point and at the time of final IMP administration will be summarized using descriptive statistics. For qualitative urinalysis parameters, shift tables will be prepared at each post-treatment time point and at the time of final IMP administration compared with baseline. In addition, for clinical laboratory test parameters other than qualitative urinalysis, measured values will be categorized as below, within, or above the normal range, and shift tables will be prepared at each post-treatment time point and at the time of final IMP administration compared with baseline.

For parameters excluding qualitative urinalysis, a scatter diagram of values after the final administration with comparison to baseline will be created.

The numbers and percentages of subjects who have a visit with serum total bilirubin value of ≥ 2 times the upper limit of normal (ULN) and an AST or ALT value of ≥ 3 times the ULN at any posttreatment time point will be calculated.

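### The SAP gives no per-arm count of subjects with any of the ten protocol-named AESI terms, or of subjects meeting either sodium withdrawal limit; the planned displays cover both only in part

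*SAP*

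**What the plan says.** **Withdrawal criteria (Protocol 3.8.3.2).** A subject must be withdrawn if "Any severe AESI (feeling abnormal, feeling hot, erythema, hyperhidrosis, pruritus, rash, urticaria, nausea, epigastric discomfort, or dyspnoea) occurs". Only severe events count here. The same list has two sodium criteria: a value of 155 mEq/L or more during treatment, and a rise of at least 12 "mEq/L from immediately predose within 24 hours after start of the IMP administration". Site or central results, in serum or plasma, can trigger either one.

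**Adverse events (SAP 9.2).** "The incidence of the following events will be summarized for all events, by SOC, and by PT". This is done for all TEAEs and by severity, death, seriousness and discontinuation, and repeated for related events. A further table shows terms reaching 2% in either arm. No grouped AESI summary is planned.

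**Sodium (SAP 9.3, 11 and 3.4).** Laboratory summaries use central results. There are descriptive statistics, a scatter plot of final against baseline values, and shift tables in which "measured values will be categorized as below, within, or above the normal range". Sodium is also a pharmacodynamic variable, with minimum and maximum of values and of changes from the Day 1 baseline. SAP 3.4 leaves discontinuation and unscheduled values out of the time-point summaries. Site sodium appears only in listing LAB-4.

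**What is counted by threshold.** SAP 9.3 counts subjects with raised bilirubin together with raised AST or ALT. SAP 9.6 counts subjects over QTcF limits. SAP 9.7 plans no other safety analysis.

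**The concern.** A secondary objective is to compare the safety of the injection with that of the tablet. Protocol 1.2.1 describes the AESI as reactions to rapid intravenous dosing not reported with oral tolvaptan, so they are the risk most specific to the new route. Rapid sodium rise is a risk in both arms, because both deliver tolvaptan. For each the protocol has already fixed a definition, yet the SAP does not tabulate subjects who meet it.

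Two features of the planned displays matter. AESI are spread over ten preferred terms, so a modest overall excess can look like scattered single cases. And a normal-range shift table records direction relative to the range, not speed: a subject who starts low and rises fast is shown as moving from low to normal.

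**Working it through.** **1. Denominator.** SAP section 4 assumes margin 0.48, SD 1.25 in both arms, no true difference, 90% power and 5% significance (two-sided). n per arm = 2 × (1.960 + 1.282)² × 1.25² / 0.48² = 142.5, so 143. With the t distribution power is 89.9% at 143 and 90.1% at 144. The stated 144 per arm (288) is reproduced and is used below. The documents give no figure for AESI or sodium-limit analyses.

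**2. Prior AESI data (Protocol 1.2.1 and 1.2.2).**

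| Infusion | OPC-61815 | Placebo |
|---|---|---|
| 1 minute | 10/11 | 4/6 |
| 5 minutes | 9/12 | 2/6 |
| 2 hours | 1/12 | 3/6 |
| 1 hour (phase 2) | 0/48, of whom 0/11 at 16 mg | – |

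The two-sided 95% upper bound for zero events in n subjects is 1 − 0.025^(1/n). It is 7.4% for n = 48 and 28.5% for n = 11. A modest rate is not excluded, and none is predicted.

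**3. AESI, no background (assumed).** Ten injection subjects with one different term each, and no tablet subject. Each term is 1/144 = 0.7%. The 2% table needs 0.02 × 144 = 2.88, so 3 subjects, and no term reaches it. Grouped: 10/144 = 6.9% against 0%, Newcombe 95% CI 2.9 to 12.3 points, Fisher p = 0.0017. Eight against none gives 5.6% and p = 0.0071.

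**4. AESI, with the documented background.** Nausea is one of the ten terms. Protocol 1.2.3 reports it in 3 of 53 (5.7%) on the 15-mg tablet; 144 × 3/53 = 8.2, about 8 subjects. Adding 8 to each arm gives 18 against 8 (12.5% against 5.6%): the same 6.9-point difference, but Fisher p = 0.06. The smaller case becomes 16 against 8, p = 0.13.

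**5. Grouping against separate terms (simulation, 144 per arm).** Assumed: one AESI per affected subject, split equally over ten terms; two-sided Fisher p < 0.05.

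| Injection vs tablet | Grouped flags | Any single term flags | No term reaches 2% on injection |
|---|---|---|---|
| 4% vs 1% | 21% | <0.1% | 81% |
| 6% vs 1% | 54% | 0.2% | 55% |
| 10% vs 2% | 78% | 2.7% | 14% |

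If five of the ten terms shared one SOC (an assumption), that row would flag the 6% vs 1% case in about 15% of trials. The tablet rates here are below the 5.7% in step 4, so the grouped column is favourable.

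**6. Sodium means.** Assumed: usual rise 2 mEq/L with SD 3, affected subjects +13. Mean shift = (difference in proportions) × (13 − 2). For 5% vs 1% (about 7 vs 1 subjects) this is 0.04 × 11 = 0.44 mEq/L, against SE = 3 × √(2/144) = 0.35. For 3% vs 0% it is 0.33; for 8% vs 2% it is 0.66.

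**7. Sodium shifts.** Exclusion criterion 11 admits sodium from 125 mEq/L. A rise from 128 to 141 is 13 and, if within 24 hours of dosing, meets the protocol limit. It appears as low to normal if 128 lies below the reference range and 141 within it (assumed; the documents give no range).

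**8. Which change is computed.** After the first dose, sodium is sampled at 4 to 6 h, 8 to 12 h and before breakfast on Day 2, so change from Day 1 is the right quantity. Later it is not. If d1, d2 and d3 are successive daily steps, the Day 4 change is d1 + d2 + d3. A step d3 of 12 or more can coexist with a smaller total if d1 + d2 is negative, and a total of 12 or more can arise with every step below 12. The protocol wording does not say whether the criterion applies to each daily dose; if it does, no planned summary computes it after the first dose.

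**The case against.** The other side is strong on several points, and most of it stands.

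- A reader might infer that these risks are analysed only by preferred terms, means and normal-range shifts. The documents do not support that. There are all-event, SOC, severity, relatedness and discontinuation tables, minimum and maximum sodium changes, a scatter plot and listings. A 13 mEq/L rise at a scheduled central sample after the first dose would show in the maximum change.
- A reader might infer that terms below 2% vanish. They do not: tables CT-8.2 and CT-8.3 have no frequency cut-off.
- Events meeting the criteria are partly tabulated. Protocol 5.1 makes a laboratory value leading to discontinuation an adverse event, so it enters the discontinuation tables. SAP 7.6 tabulates subjects who met a withdrawal criterion but stayed in. The last-available-value rule in SAP 5.5 may also bring some withdrawal results into the final-time-point laboratory row. But none of these gives a count for each limit, and mild or moderate AESI need not lead to withdrawal.
- A reader might carry the bolus rates over to this trial. The documents point the other way: placebo rates were also high, the two-hour infusion gave 1 of 12, and the one-hour infusion gave none.
- A crude composite can dilute the signal. Nausea occurs on the tablet, and dyspnoea is a symptom of heart failure (Protocol section 1). This stands, and is why a related or infusion-timed version is needed.
- Pooling site and central sodium without a rule would mix plasma with serum. This also stands.
- Protocol 7.6 plans neither analysis, so the SAP breaks no commitment.

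**Conclusion.** The gap is real but limited. No planned table gives, by arm, the number of subjects with any of the ten AESI terms or over either sodium limit, while the same SAP does this for liver and QTcF thresholds. Existing displays would let a careful reader find much of the information, but not the count. For sodium, central-only scheduled values and change from Day 1 leave part of the protocol's own definition uncomputed.

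It would go too far to say that the plan conceals an excess, or that one is expected. The size rests on assumed rates. Under a zero tablet rate, 10 against 0 gives p = 0.002; with the documented tablet nausea rate the same excess gives 18 against 8 and p = 0.06. Even grouped, the chance of flagging an excess runs from 21% to 78% over the rates tried, so the counts are for description, not for a test. The primary non-inferiority conclusion is not touched. This is an inexpensive improvement to a stated safety comparison.

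**What to change.** **SAP 9.2.** Add one table by arm of subjects with at least one of the ten AESI terms: any grade; severe; and IMP-related or with onset during or soon after the infusion. Give the difference and 95% CI for each row. Before unblinding, fix the list of MedDRA terms and the onset window. Infusion times and causality are recorded, and onset times are recorded in hospital whenever possible.

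**SAP 9.3.** Add per-arm counts for each sodium limit separately. Take the rise from the same day's predose value, and show the first-dose interval on its own so that the table serves either reading of the criterion. Include discontinuation and unscheduled values. Show central serum and site (serum or plasma) results separately and as either source, and never compute one change across two sources.

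**Cost.** Two extra descriptive tables from data already on the eCRF and in the laboratory file, with some background noise in the any-grade composite. There is no new data collection, no change in sample size, no multiplicity claim, and no change to any withdrawal rule.

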9.3 Clinical Laboratory Data

Clinical laboratory data obtained from central measurements will be used.

For hematology, serum chemistry (excluding PAP and TRACP-5b), and urinalysis in the protocol “Table 3.7.3.2-1 Clinical Laboratory Assessments”, the following will be summarized.

For clinical laboratory test parameters other than qualitative urinalysis, measured values and changes from baseline at each time point and at the time of final IMP administration will be summarized using descriptive statistics. For qualitative urinalysis parameters, shift tables will be prepared at each post-treatment time point and at the time of final IMP administration compared with baseline. In addition, for clinical laboratory test parameters other than qualitative urinalysis, measured values will be categorized as below, within, or above the normal range, and shift tables will be prepared at each post-treatment time point and at the time of final IMP administration compared with baseline.

For parameters excluding qualitative urinalysis, a scatter diagram of values after the final administration with comparison to baseline will be created.

The numbers and percentages of subjects who have a visit with serum total bilirubin value of ≥ 2 times the upper limit of normal (ULN) and an AST or ALT value of ≥ 3 times the ULN at any posttreatment time point will be calculated.

9.4 Vital Sign Data

For vital signs, measured values and changes from baseline at each time point and at the time of final IMP administration will be summarized using descriptive statistics.

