The expected adverse drug reactions of tolvaptan are important information for predicting the adverse drug reactions of OPC-61815. In clinical trials involving patients with cardiac edema (Trials 156-03-001, 156-06-002, 156-06-004, 156-06-006, 156-10-005, 156-12-809-01, and 156-TWA-1101), the frequently reported AEs (with a $\geq 2\%$ incidence, and higher than that in the placebo group) in 437 subjects treated with tolvaptan tablet were ventricular tachycardia, constipation, dry mouth, diarrhoea, vomiting, thirst, malaise, blood urea increased, blood uric acid increased, blood creatinine increased, blood potassium increased, blood sodium increased, blood glucose increased, blood urine present, platelet count decreased, blood pressure decreased, dehydration, hyperkalaemia, dizziness, headache, dizziness postural, pollakiuria, renal impairment, and epistaxis. For details regarding the AEs related to tolvaptan that have been reported in clinical trials, see the IB.

2 Trial Rationale and Objectives

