3.4.3 Exclusion Criteria

Subjects will be excluded if they meet any of the exclusion criteria in [Table 3.4.3-1](#).

Table 3.4.3-1 Exclusion Criteria	
1	Patients with acute heart failure
2	Patients with mainly noncardiogenic congestive symptoms
3	Patients who are on a ventricular assist device
4	Patients who have any of the following diseases, complications, or conditions: 
 • Suspected hypovolemia • Hypertrophic cardiomyopathy (excluding dilated phase) • Valvular disease with significant valvular stenosis • Hepatic encephalopathy with difficulty in adequate fluid intake
5	Patients who have experienced acute myocardial infarction within 30 days prior to the screening examination
6	Patients with a definite diagnosis of active myocarditis or amyloid cardiomyopathy
7	Patients who have any of the following diseases, complications, or conditions: 
 • Poorly controlled diabetes mellitus • Anuria • Dysuria associated with urinary tract obstruction, calculus, or tumor
8	Patients who have any of the following medical histories: 
 • History of sustained ventricular tachycardia or ventricular fibrillation within 30 days prior to the screening examination (for patients without an implantable cardioverter defibrillator) • History of cerebrovascular disease (excluding asymptomatic cerebral infarction) within 6 months prior to the screening examination • History of hypersensitivity or idiosyncratic reaction to benzodiazepines or benzodiazepine derivatives such as the ingredients of OPC-61815, tolvaptan, mozavaptan hydrochloride, and benazepril hydrochloride
9	Patients who are severely obese (body mass index [BMI] = body weight [kg]/height [m] ² exceeding 35 kg/m ²)
10	Patients with supine systolic blood pressure of <90 mmHg
11	Patients with any of the following abnormalities in laboratory test results: Total bilirubin >3.0 mg/dL, serum creatinine > 3.0 mg/dL, serum Na <125 mEq/L and >147 mEq/L, and serum K >5.5 mEq/L

Table 3.4.3-1 Exclusion Criteria	
12	Patients with current symptoms or a history of hepatic impairment (including patients with aspartate aminotransferase [AST] or alanine aminotransferase [ALT] exceeding 3 times the upper limit of the reference range at the screening examination)
13	Patients who are unable to sense thirst or who have difficulty with fluid intake

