14	Female patients who are breast-feeding or who have a positive pregnancy test result prior to receiving IMP
15	Sexually active males or women of childbearing potential (WOCBP) who do not agree to practice birth control or remain abstinent during the trial and for 30 days after the final IMP administration.
16	Patients who have received tolvaptan within 28 days prior to the screening examination
17	Patients who have participated in a clinical trial in which they received OPC-61815
18	Patients who have participated in another clinical trial and received another IMP within 30 days prior to the screening examination
19	Patients who are otherwise judged to be ineligible by the investigator or subinvestigator

Nonchildbearing potential is defined as male and female subjects who are surgically sterile (ie, male subjects who have undergone bilateral orchidectomy and female subjects who have undergone bilateral oophorectomy and/or hysterectomy) and female subjects who have been postmenopausal for at least 12 consecutive months.

Subjects must agree to the restrictions to concomitant medications as described in [Section 4](#).

Subjects who sign an ICF but are not assigned to IMP are permitted to be re-screened one more time. In the event that the screening assessment is repeated, a new ICF signed by the subject must be obtained and a new subject identifier will be assigned to the subject.

[Rationale for the exclusion criteria]	
1	This criterion is set because the rapid onset or worsening of the symptoms may hinder the conduct of the trial.
2	The criterion is set because the proposed target patient population of OPC-61815 is patients who have volume overload associated with CHF.
3	The use of a ventricular assist device may affect the efficacy or safety assessment of the IMPs.
4	Excessive diuretic treatment may adversely affect these symptoms.
5, 6	These criteria are based on safety considerations.
7	This criterion is based on safety considerations and set to exclude patients ineligible for participation in the trial.
8	These criteria are based on safety considerations.
9	This condition may hinder the efficacy assessment of the IMPs.
10	Blood pressure may decrease due to diuresis.

11 to 13	These criteria are based on safety considerations.
14 and 15	These criteria are based on general safety and ethical considerations.
16 and 17	The use of the IMPs may affect the efficacy or safety assessment of the IMPs.

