3.7.3.3 Physical Examination and Vital Signs

1) Physical examination

The investigator or subinvestigator will check the physical conditions of the subject by interview and other methods at the prespecified time points. The physical examination includes the observation of the head, ears, eyes, nose and pharynx, chest, abdomen, genitourinary tract, extremities, nerves, and skin/mucosae. At the screening examination, the date and the results of assessment will be recorded in the source document and the eCRF. At subsequent assessments, only the date of assessment will be recorded in the source document and the eCRF. A clinically important physical

finding that is absent at the screening examination but observed at any post-treatment assessment will be recorded as an AE.

2) Vital signs (blood pressure, pulse rate, and body temperature)

At the prespecified time points, axillary temperature will be measured after the subject is kept rested according to the procedures specified by the trial site. Blood pressure (systolic and diastolic) and pulse rate will be measured after the subject is kept supine for at least 3 minutes. The measurement result of body temperature should be rounded to the first decimal place for recording, even if the measurement result is shown the second decimal place or more. The date and time, and the results of measurements will be recorded in the source document and the eCRF.

3.7.3.4 12-Lead Electrocardiogram Assessments

At the prespecified time points, a rest 12-lead electrocardiogram (ECG) will be recorded using the ECG monitor provided by the central ECG measurement facility and according to the procedure specified by the facility. However, if the serum potassium concentration at the trial site or the central laboratory is confirmed to exceed 5.5 mEq/L at any time point with no specified 12-lead ECG during the treatment period, an additional 12-lead ECG will be performed as an unscheduled examination. The investigator or subinvestigator will interpret each ECG chart as normal or abnormal, and record the status (measured/ not measured), the date of recording, as well as the interpretation (normal or abnormal [details, if abnormal]) in the source document and the eCRF.

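### The SAP plans no per-arm, any-time count of subjects with low systolic pressure, high potassium or raised creatinine, so an excess in one arm can be missed unless it is reported as adverse events.

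*SAP*

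**What the plan says.** **Known harms.** Protocol 1.3 says tolvaptan's reactions are important for predicting those of OPC-61815. Its list of frequent events in tolvaptan trials includes "blood creatinine increased, blood potassium increased, blood sodium increased" and "blood pressure decreased, dehydration, hyperkalaemia, dizziness, headache, dizziness postural, pollakiuria, renal impairment, and epistaxis". The rationale for exclusion criterion 10 (Protocol 3.4.3) adds: "Blood pressure may decrease due to diuresis".

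**Values named in the documents.**
- Systolic pressure: exclusion criterion 10, "Patients with supine systolic blood pressure of <90 mmHg". Entry only.
- Creatinine: above 3.0 mg/dL is an exclusion (criterion 11). The SAP uses 2 mg/dL to split baseline values and subgroups (SAP 7.3, 8.4).
- Potassium: above 5.5 mEq/L is an exclusion. It is also used on treatment, because Protocol 3.7.3.4 calls for an extra ECG "if the serum potassium concentration at the trial site or the central laboratory is confirmed to exceed 5.5 mEq/L".

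**Planned summaries.**
- Vital signs (SAP 9.4): "For vital signs, measured values and changes from baseline at each time point" and at final administration, by descriptive statistics. CT-11 is the only vital-sign table in Appendix 1.
- Laboratory (SAP 9.3): descriptive statistics, a final-versus-baseline scatter plot, and categories: "measured values will be categorized as below, within, or above the normal range, and shift tables will be prepared". The one subject-level threshold count combines bilirubin with AST or ALT.
- ECG (SAP 9.6): subjects above set QTc levels or changes at any post-treatment time are counted by arm.
- SAP 3.4 leaves out unscheduled values, and drops discontinuation values from the by-visit summaries.

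**The concern.** These harms tend to appear as marked changes in a few subjects. A mean over 144 subjects barely moves when a handful change, and moves less when the changes fall on different days. A three-category shift table has only one cell for everything above normal.

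Comparing safety with the tablet is part of the stated secondary objective. If more subjects are affected in one arm, the planned blood pressure and laboratory tables may not show it. A reader would then depend on whether investigators recorded those changes as adverse events. The SAP already uses the more sensitive summary for QTc and liver tests, and gives no reason for leaving it out here.

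**Working it through.** The documents give no figure on this point. The sample size supplies only the arm size, n = 144.

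**1. What each planned output can show**

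- *Blood pressure.* Scheduled on five mornings after dosing starts (Days 2 to 6) and at follow-up. There is no category of any kind. The minimum (SAP 7.2 defines the descriptive statistics) shows the single lowest reading, not how many subjects had a low one.
- *Potassium.* Scheduled on treatment seven times (4 to 6 h, 8 to 12 h, Days 2 to 6) and at follow-up. Normal-to-high shifts are tabulated at each time point (CT-10.3.2), but by-visit cells do not add up to subjects ever affected.
- *Creatinine.* Scheduled on Day 1, at Day 6 or withdrawal, and at follow-up, so there is one scheduled on-treatment value. Values up to 3.0 mg/dL are eligible. As an example, assume 2.1 mg/dL is above the normal range. A rise from 2.1 to 2.9 mg/dL is (2.9 − 2.1)/2.1 = 38%, yet it stays in the above-to-above cell.

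**2. How far a mean moves (all inputs assumed)**

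Take a 5-point excess in one arm, 0.05 × 144 ≈ 7 subjects. The shift in the mean is 0.05 × size of change, divided by the number of time points if the changes are spread evenly. The yardstick is the 95% half-width of a mean difference, 1.96 × SD × √(2/144). The SAP does not plan this interval for these data.

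- Blood pressure, 25 mmHg fall: 0.05 × 25 = 1.25 mmHg at one visit, or 1.25/5 = 0.25 if spread. Half-width 2.8 to 3.5 for SD 12 to 15.
- Potassium, rise of 0.8 mEq/L: 0.05 × 0.8 = 0.04 at one sample, or 0.04/7 = 0.006 if spread. Half-width 0.08 to 0.12 for SD 0.35 to 0.5.
- Creatinine, rise of 0.5 mg/dL: 0.05 × 0.5 = 0.025. Half-width 0.046 to 0.069 for SD 0.2 to 0.3.

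Each shift is smaller than its half-width.

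**3. What a count would show**

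With 12 versus 3 affected of 144 (assumed):

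- Count: 8.3% versus 2.1%, a difference of 9/144 = 6.3 points. Wald 95% CI 1.2 to 11.3; Fisher p = 0.031.
- Mean, if each affected subject has one 30 mmHg fall: 30 × 9/144 = 1.9 mmHg at one visit, or 0.4 mmHg spread over five. At SD 15 the standard error is 15 × √(2/144) = 1.77, so the shift is 1.1 or 0.2 standard errors.

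With only 7 extra subjects the count is less decisive: Fisher p = 0.060 (9 versus 2), 0.085 (10 versus 3) and 0.15 (13 versus 6). It still puts the number of affected subjects in front of the reader.

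**The case against.** The strongest reply is the adverse event analysis. SAP 9.2 gives incidence by arm and preferred term, by severity, for serious events and for events leading to discontinuation, plus a table of events reaching 2% in any group. For an arm of 144 that is 0.02 × 144 = 2.9, so 3 subjects. Seven extra subjects under one preferred term would appear there. This stands, and a reader who inferred that an excess would be hidden would go too far. What remains is that, under Protocol 5.1, a laboratory change that neither leads to discontinuation nor meets a seriousness criterion becomes an adverse event only if the investigator considers it medically relevant.

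A reader might also infer that the protocol sets on-treatment safety limits for all three measures. It does not. Systolic pressure below 90 mmHg and creatinine above 3.0 mg/dL are entry criteria, 2 mg/dL is a baseline and subgroup split, and no limit for renal worsening is stated. Only potassium above 5.5 mEq/L is used on treatment.

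The point about changes falling on different days does not apply to creatinine, which has one scheduled on-treatment sample. The scatter plot shows each subject's creatinine change, though without a count. Minimum and maximum, the abnormal-findings listing (CT-10.4.1) and the subject listings of vital signs and potassium (PDATA-5.1, PDATA-10) are further partial safeguards. None gives the number affected in each arm.

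**Conclusion.** The gap is real and modest. The SAP plans no any-time count by arm of subjects beyond a systolic pressure, potassium or creatinine value, while it plans such counts for QTc and liver tests. Planned summaries can miss an excess that is not reported as adverse events. This is clearest for blood pressure and for creatinine in subjects already above normal, and weaker for potassium.

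The documents do not support saying that the safety comparison will look falsely balanced. Every size shown rests on assumed event numbers, changes and SDs, and an excess of about 7 subjects would not give a Fisher p below 0.05 in the cases shown. Making the change is still worthwhile: it is cheap, uses a summary the SAP already applies elsewhere, and serves the stated secondary comparison. The primary analysis is untouched.

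**What to change.** Add to SAP 9.3 and 9.4, as reporting categories only with no change to patient care. For (a) and (b), give numbers and percentages by arm, with the arm difference and exact 95% CI as in SAP 8.3:

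- (a) central serum potassium above 5.5 mEq/L at any post-treatment time point, among subjects at or below 5.5 on Day 1. This is the protocol's own ECG trigger value. Site results do not enter the eCRF (Protocol 3.7.3.2), so the count will not equal the number of triggers.
- (b) supine systolic pressure below 90 mmHg at any post-treatment time point, among subjects at or above 90 on Day 1, described as the entry limit reused for description.
- (c) creatinine: descriptive statistics of percent change from baseline at final administration by arm, with no CI on the distribution. Crossing 2 and 3.0 mg/dL are supplementary counts only, because a rise from 2.1 to 2.9 or from 1.0 to 1.9 crosses neither.

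State that the any-time counts include withdrawal-assessment values and unscheduled central laboratory values despite SAP 3.4. Otherwise affected subjects could still drop out of them. The on-treatment sodium criteria in Protocol 3.8.3.2 (a rise of at least 12 mEq/L within 24 hours, or a value of at least 155 mEq/L) can be counted in the same way.

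The cost is SAP wording and a few table rows from data already collected. The downside is a few more descriptive comparisons without multiplicity control.
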